6.4.2 Corneometer assessment

Corneometer is one of the most popular measurement instrument to reproducibly and accurately determine the hydration level of the skin surface (stratum corneum).

The corneometer indicates the hydration level of the superficial layers of the skin via measurement of skin dielectric properties.

The measurements are performed by the application of a probe to the skin surface. Upon contact, an electric field passes through the stratum corneum and the dielectric constant is obtained.

The value of the dielectric constant (in arbitrary units) is directly proportional to the level of skin hydration.

On the probe head there is a fine piece of glass to ensure that only the capacitance changes due to water content are identified. Even small changes in water can be detected. The measurement time is short at only 1 second minimising occlusion effects. The depth of the measurement is 10-20µm, therefore limited to the stratum corneum, ensuring that deeper skin layers do not influence the measurement.

The measuring surface is around 49mm², so even small areas can be accurately measured.

6.4.3 Skin texture, skin tone, fine lines and wrinkles assessment

The Investigator will evaluate at each visit the skin texture, skin tone, smoothing of fine lines and wrinkles modification in the treated area and will score each item as follows:

| | Poor | Good | Very good |
|--------------|------|------|-----------|
| Skin texture | | | |
| | Poor | Good | Very good |
| | | | |

| | Poor | Sufficient | Middle | Good |
|-----------|------|------------|--------|------|
| Skin tone | | | | |

CONFIDENTIAL Page 27 of 51

Wrinkles will be assessed through the severity rating scale:

| Grade | Description |
|-------|-------------|
| 1 | Absent |
| 2 | Slight |
| 3 | Moderate |
| 4 | Severe |
| 5 | Extreme |

6.4.4 Global Aesthetic Improvement Scale (GAIS) by the Investigator

GAIS is a categorical scale with five levels:

| Grade | Description |
|-------|-----------------------------|
| 1 | worse than before treatment |
| 2 | no change |
| 3 | minimal improvement |
| 4 | good improvement |
| 5 | optimal improvement |

The Investigator will be requested to judge the aesthetic improvement of the treated area at all visits following the first one.

6.4.5 Patient's Aesthetic Improvement Scale (PAIS)

PAIS is a categorical scale with five levels:

| Grade | Description |
|-------|---------------------|
| 1 | worse |
| 2 | no change |
| 3 | somewhat improved |
| 4 | moderately improved |
| 5 | very much improved |

The subject will be requested to judge the aesthetic improvement of the treated area at all visits following the first one.

6.4.5 Subject Overall Satisfaction

Overall subject's satisfaction on the treatment received will be defined by means of a 5items scale at the end of the study (Visit 4).

CONFIDENTIAL Page 28 of 51

The subject will be asked "Please express your degree of satisfaction with the treatment received"

| Grade | Description |
|-------|-------------------------------|
| 1 | very much satisfied |
| 2 | satisfied |
| 3 | not satisfied nor unsatisfied |
| 4 | unsatisfied |
| 5 | very unsatisfied |

6.5 Monitoring Plan

The study will be monitored on a regular basis by the CRO's adequately qualified and trained clinical Monitors throughout the study period to ensure the proper conduct of the clinical Investigation.

The purposes of study monitoring are to verify that the rights and well-being of study subjects are protected, that the reported study data are accurate, complete and verifiable against the source documents, and that the study is conducted in accordance with the current clinical investigation plan, Good Clinical Practice guideline (UNI EN ISO 14155) and applicable regulatory requirements.

During the monitoring visits, Monitors will verify the following, including but not limited to: subject informed consent, subject's eligibility, safety data and reporting, quality of source documents and CRF data against subject's medical records. If inconsistencies are found, the corresponding corrections to the CRF data will have to be made by the Investigator or designated person. Monitors will also check subject compliance, accrual, delegation of responsibilities within the Investigator's team, relevant communications with family doctors, if any, ancillary equipment and facilities, etc. The Investigator and other site staff involved in the study must allocate enough time to the Monitor at these visits.

Given the current COVID-19 pandemic situation also proper approaches will be implemented remotely to allow the performance of the monitoring activities, in line with applicable guidelines of competent authorities and best practices.

Upon request by the Sponsor, on-site study audits may be conducted in order to ensure the study is in compliance with GCP, applicable regulatory requirements, and the clinical investigation plan. The auditing activities may also be conducted after study completion.

CONFIDENTIAL Page 29 of 51

The Investigator agrees to allow Sponsor/auditors/CRO monitors to have direct access to his/her study records for review, being understood that they are bound by professional secrecy, and as such will not disclose any personal identity or personal medical information.

The Investigator will take all appropriate measures required by the Sponsor to implement corrective actions for all problems found during audits.

7. Statistical Design and Analysis

This section summarizes the statistical principles and methods planned to analyze the data for this clinical investigation.

7.1 Sample Size Determination

Assuming an average difference in the skin hydration evaluated through corneometer skin examination (capacitance) between baseline and Day 98 of 7.5, with a standard deviation of 8, 20 subjects will allow to appreciate this difference as statistically significant at an alpha = 0.05 and a 95% power. Considering the above and a possible drop-out rate of 20%, 24 subjects will be recruited.

7.2 Definition of Study Populations for Analysis

The following populations are defined for this investigation:

- Safety analysis set (SAF): all subjects enrolled who sign informed consent and receive at least one administration of the investigational device.
- Full analysis set (FAS): all subjects of the SAF who have performed the baseline assessments and have at least one post-baseline assessment of any performance endpoint (primary or secondary).
- Per-Protocol analysis set (PPAS): all subjects of the FAS who also meet all inclusion/exclusion criteria and who do not have any major protocol deviation.

The analysis of safety endpoints will be performed in the SAF population. Analysis of performance endpoints will be performed on the FAS population. Additionally, analysis of primary endpoint will also be performed on the PPAS population.

CONFIDENTIAL Page 30 of 51

7.3 Statistical Analysis

Descriptive statistical analysis of all relevant variables will be performed. Continuous variables will be summarized by the number of subjects (N), mean, standard deviation, median, minimum, maximum. Categorical variables will be summarized by the number (N) and the proportion of subjects (%). Where appropriate, 95% confidence intervals for the target variables will be estimated.

The significance level of statistical tests will be set at 0.05. Parametric tests (e.g., paired t-test) will be used to analyze continuous variables; when continuous variables are not normally distributed, the corresponding non-parametric tests (e.g., Wilcoxon signed rank test) will also be performed. Details of statistical analysis are provided in the following paragraphs.

The statistical analysis will be performed using SAS 9.4 for Windows (SAS Institute Inc., Cary, NC, USA).

7.3.1 Missing Data

Missing data will not be replaced in any statistical analysis.

7.3.2 Multiplicity

No adjustment is needed.

7.3.3 Covariates, Interactions and Subgroups

There are no planned subgroup analyses.

7.3.4 Analysis of Demographics and Baseline Variables

Demographic (gender, age) and baseline characteristics will be summarized using mean, median, standard deviation, minimum and maximum for continuous variables and frequencies and percentages for categorical variables.

CONFIDENTIAL Page 31 of 51

7.3.5 Efficacy analysis

7.3.5.1 Primary endpoint

Paired t-test, when the skin hydration is normally distributed, or the corresponding non-parametric Wilcoxon signed rank test will be used to assess a significant change in skin hydration, evaluated through corneometer skin examination (capacitance), from baseline to Day 98.

7.3.5.2 Secondary endpoints

Paired t-test, when the skin hydration is normally distributed, or the corresponding non-parametric Wilcoxon signed rank test will be used to assess a significant change in skin hydration, evaluated through corneometer skin examination (capacitance), from baseline to Day 21 and Day 42.

Subjects will be considered responders when skin hydration increase is at least 10% between baseline and Day 98 and non-responders when there is not any increase in skin hydration. The number (N) and proportion of subjects (%) for each category will be reported.

The skin texture, skin tone, smoothing of fine lines and wrinkles will be summarized at all time-points in terms of number (N) and percentage (%). Subjects will be considered responders when Investigator's evaluation of skin texture, skin tone and smoothing of fine lines increases at least one category on the assessment scale, from baseline; otherwise, subjects will be considered non-responders. Subjects will be considered responders when Investigator's evaluation of wrinkles decreases at least two grades on the severity rating scale, from baseline; otherwise, subjects will be considered non-responders. Subjects whose grade on the severity rating scale of Investigator's evaluation of wrinkles decreases from 2 "Slight" to 1 "Absent" will also be considered responders.

The Global Aesthetic Improvement Scale (GAIS) filled-in by the investigator and the Patient's Aesthetic Improvement Scale (PAIS) filled-in by the subject will be summarized at all time-points in terms of number (N) and percentage (%). Subjects will be considered responders when the evaluation increases at least one level on the categorical scale, from baseline; otherwise, subjects will be considered non-responders

CONFIDENTIAL Page 32 of 51

The overall subject's evaluation of satisfaction with the treatment at Day 98, performed by means of the 5-item scale, will be summarized through number (N) and proportion of subjects (%) for each item.

7.3.6 Safety Analysis

All enrolled subjects receiving at least one treatment injection will be included in the safety analysis.

Adverse events (AEs) and Adverse Device Events (ADEs) will be coded using the last updated version of the Medical Dictionary for Regulatory Activities (MedDRA) dictionary to give a preferred term (PT) and a system/organ class term (SOC) for each event. The number of subjects who experienced at least one AE or ADE, study product-related AE or ADE, serious AE or ADE, severe AE or ADE and the number of subjects withdrawn due to AE will be summarized.

For each SOC and preferred term, summaries will be made with respect to the proportion of subjects having at least one occurrence of that event during the study and the total number of events. The incidence of AEs and ADEs will be presented overall, by SOC and preferred term, and additional grouping by severity and relationship to the study treatment.

Local tolerability at the site of administration will be reported and summarized.

7.4 Planned Interim Analysis

No interim analysis is planned.

8. Data Management

During each study visit, the study Investigator (or designee) will collect and report study data in the relevant subject's chart, documenting all significant observations.

Any contact with the subject via telephone or other means that provides significant clinical information shall be documented in the source data.

An Electronic Case Report Form (e-CRF) will be used to record subject's study data.

All data relating to the study will be documented in the electronic CRF (e-CRF). This CRF is developed to record the data requested by the protocol.

The Investigator will maintain a list of all persons authorized to make entries and/or corrections on the e-CRFs. Each authorized person will be provided with a user-specific

CONFIDENTIAL Page 33 of 51

ID protected by a renewable password. Data entries and corrections will be made only by the authorized persons. The e-CRF system will record date and time of any entry and /or correction and the user ID of the person making the entry/correction. The system will keep track of all old and new values (audit trail). It is the responsibility of the Investigator to ensure that the CRFs are properly and completely filled in. The CRFs must be completed for all subjects who have been included in the study. The Investigator will review all CRFs and electronically sign and date them for each subject, verifying that the information is complete, true and correct. All fields on the CRF must be completed as applicable.

Checks to assist during the data entry and to assess the appropriateness and consistency of data will be developed on the e-CRF system. E-CRF pages will be reviewed both on site by the monitor of the center and remotely, by the data management staff of the CRO. Data Clarification Sheets (DCS) will be generated through the e-CRF system, both automatically, through edit checks, and manually, by CRAs and/or data managers, and the Investigator will have to check and solve them. The Investigator is responsible for the review and approval of all guery resolutions.

Subjects will be provided with paper questionnaires/scales. Such documents will be filled by the subjects during the study visits, to record data concerning their opinion on the aesthetic result of the treatment and the consequent satisfaction with the treatment received.

It is responsibility of the Investigators to instruct the study participants on how to fill in questionnaires in a clear way and preferably in black ball-point pen. The questionnaires/scales will be anonymous, each subject is identified through the Subject Code. Questionnaires/scales data will be reported on the e-CRF by the Investigator (or designee). Questionnaires will be considered source data.

At the beginning of the study, a Study Master File will be established according to Sponsor or CRO SOPs, in order to maintain the study documents as specified in the UNI EN ISO 14155 Guideline and as required by the applicable regulatory requirements. The CRO will take measures to prevent accidental or premature destruction of these documents.

Clinical sites will permit study-related monitoring, audits, and regulatory inspection providing direct access to source data / documents.

CONFIDENTIAL Page 34 of 51

Essential documents of the clinical investigation, including the subject identification list, source data and case report forms will be retained for 10 years after the completion or discontinuation of the clinical investigation at clinical sites. The sponsor will retain the study master file for 10 years after the CE mark for the study product has been discontinued in all countries.

9. Amendments to the CIP

Changes to the clinical investigation plan may only be made by means of a written amendment, which has to be approved and signed by the authorized representatives of the Sponsor, and by the Investigator.

Exhaustive justifications that motivate the amendment to the clinical investigation plan should clearly be addressed in the document.

All substantial Clinical Investigation Plan amendments must be submitted for approval to IEC and notified to the Regulatory Authority. In case of non-substantial amendment the IEC and the Regulatory Authority (when applicable) will be only notified of the amendment without the request to review and approve it.

The Investigator, the Sponsor and IEC, separately or together, should decide whether the subject's informed consent form needs to be changed.

10. Deviations from Clinical Investigation Plan

The Investigator is to conduct the study in accordance with the relevant, current clinical investigation plan and will only deviate when necessary to protect the safety, rights and welfare of the subjects. In the event that an isolated, unforeseen instance occurs resulting in a clinical investigation plan deviation, the Investigator is to document this deviation and notify the CRO or the Sponsor as soon as possible. In no instance should this increase the subject's risk or affect the validity of the study.

CONFIDENTIAL Page 35 of 51

11. Device Accountability

The device will be administered only at clinical site under the responsibility of the Investigator. The Investigator is responsible of ensuring the correct device administration and for registering data of the treatment administered.

The study product will be provided to the clinical site once ethical authorization is obtained.

12. Statement of Compliance

The study will be conducted in compliance with the current version of the Declaration of Helsinki (Appendix 2), with the clinical investigation plan, the MDR 745/2017, the UNI EN ISO 14155, the Italian laws in force and the principles of the Good Clinical Practice. The clinical investigation will start at clinical site only after obtaining the approval of the relevant Ethics Committee.

13. Informed Consent Process

The Investigator is responsible for and will obtain informed consent from each subject, in accordance with the UNI EN ISO 14155, and the current version of the Declaration of Helsinki.

All subjects invited to participate in the study are entitled to make their voluntary decision based on all current available information provided to them by the Investigator/designee. In addition, they will be given a document in native language written in clear concise lay language for review and consideration. The document will previously have been approved by the relevant independent Ethics Committee (IEC) and may further be updated as new important information becomes available that may affect subject's willingness to participate or continue in the study.

The subject must be made aware that he/she may refuse to join the study or may withdraw his/her consent at any time without prejudicing further medical care and that he/she is covered by the Sponsor's indemnity insurance in the event of a study related injury. Subjects must also know that their personal medical records may be reviewed in confidence by the Sponsor's staff or representatives and by Regulatory Authority and

CONFIDENTIAL Page **36** of **51**

IEC and that personal information will be collected and retained in a confidential database. Consent will always be given in writing after the subject has had adequate time to review the information and ask questions, if need be.

14. Adverse Events, Adverse Device Effects and Devices Deficiencies

14.1 Definitions

Adverse Event (AE)

Any untoward medical occurrence, unintended disease or injury or any untoward clinical signs, including an abnormal laboratory finding, in subjects, users or other persons, in the context of a clinical investigation, whether or not related to the investigational device.

Adverse Device Effect (ADE)

Any untoward and unintended response to a medical device. This includes any event resulting from insufficiencies or inadequacies in the instructions for use or the deployment of the device and any event that is a result of a user error.

Device Deficiency

Any inadequacy in the identity, quality, durability, reliability, safety or performance of an investigational device, including malfunction, use errors or inadequacy in information supplied by the manufacturer.

Serious Adverse Event (SAE)

Any adverse event that led to any of the following:

- a) death,
- b) serious deterioration in the health of the subject, that resulted in any of the following:
 - i. life-threatening illness or injury,
 - ii. permanent impairment of a body structure or a body function,
 - iii. hospitalisation or prolongation of patient hospitalisation,
 - iv. medical or surgical intervention to prevent life-threatening illness or injury or permanent impairment to a body structure or a body function,
 - v. chronic disease
- c) foetal distress, foetal death or a congenital physical or mental impairment or birth defect.

CONFIDENTIAL Page 37 of 51

Serious Adverse Device Effect (SADE)

Adverse device effect that has resulted in any of the consequences characteristic of a serious adverse event or that might have led to any of these consequences if suitable action had not been taken or intervention had not been made or if circumstances had been less opportune.

Unanticipated Serious Adverse Device Effect (USADE)

Serious adverse device effect that by its nature, incidence, severity or outcome has not been identified in the risk analysis report.

Incident

Any malfunction or deterioration in the characteristics and/or performance of a device, as well as any lack of labelling or instructions for use which, directly or indirectly, may cause or have caused death or serious deterioration in the health of the patient or of a user or of other persons.

14.2 Adverse Event Intensity/Causality

The Investigator, based on his direct observation or on subjects' report, will record the event according to the current version of CTCAE:

| Description | Definition |
|---|---|
| Grade 1 (Mild): | asymptomatic or mild symptoms; clinical or diagnostic observations only; intervention not indicated. |
| Grade 2 (Moderate): | minimal, local or noninvasive intervention indicated; limiting age- appropriate instrumental daily life activities. |
| Grade 3 (Severe): | medically significant but not immediately life-threatening; hospitalization or prolongation of hospitalization indicated; disabling; limiting self -care daily life activities. |
| Grade 4 (Life- threatening consequences): | urgent intervention indicated. |
| Grade 5: | death related to AE |

CONFIDENTIAL Page 38 of 51

The relationship of any AE to the product will be classified by the Investigator as follows:

| Description | Definition |
|---------------------|--|
| Not related | Relationship to the device, comparator or procedures can be excluded. |
| Probable | The relationship with the use of the investigational device or comparator, or the relationship with procedures, seems relevant and/or the event cannot be reasonably explained by another cause. |
| Possible | The relationship with the use of the investigational device or comparator, or the relationship with procedures, is weak but cannot be ruled out completely. |
| Causal relationship | The adverse event is associated with the investigational device, comparator or with procedures beyond reasonable doubt. |

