Today, intradermal injections of biological substances able to induce a revitalization of the dermis can stimulate qualitative and quantitative improvements in aging skin alterations. The most frequently used substance is natural noncross-linked hyaluronic acid (HA), which is the main ingredient of the medical device Foliage Hydrofil.

The aim of this study is to confirm the clinical performance and safety of the medical device Foliage Hydrofil on the face bio-revitalizing treatment. To this purpose no. 24 adults (males and females) searching for bio-revitalization treatment will be enrolled and treated with three injective sessions apart 3 weeks each other. All the subjects will receive the same treatment in an open label fashioned study.

4. Benefits and Risks of the Investigational Device, Clinical Procedures and Clinical Investigation

Foliage Hydrofil belongs to a class of minimally invasive treatments used to maintain a youthful appearance. All the subjects will be treated in the face sites agreed with the physician.

The product will be injected through micro-injections in the derma. Injections, even if done with micro needles could generate some risks and a certain level of discomfort to the subject. In order to avoid risks, the Investigator will duly disinfect the injection sites before treatments. If necessary, an anesthetic cream could be used before injections. Potential side effects due to the treatment are mainly pain, erythema, edema, bruising, but they are usually of mild intensity and transient. In such cases the Investigator will suggest the appropriate treatment to manage any side effect.

CONFIDENTIAL Page 17 of 51

No tests or invasive examinations are foreseen in this study that can increase the risk for participants.

In the light of the above, no additional risk arising from the participation to this clinical investigation can be envisioned.

5. Objectives and Hypotheses of the Clinical Investigation

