# STATISTICAL ANALYSIS PLAN TEMPLATE

Statistical Analysis Plan Version no. 1.0 – 20/03/2023 Clinical Investigation Plan Code FOLIAGE - 2022 EudraCT number NA

study product-related AE or ADE, serious AE or ADE, severe AE or ADE and the number of subjects withdrawn due to AE will be summarized in the Table 3.1.

For each SOC and preferred term, summaries will be made with respect to the proportion of subjects having at least one occurrence of that event during the study and the total number of events. The incidence of AEs and ADEs will be presented overall, by SOC and preferred term, and additional grouping by severity and relationship to the study treatment in the Table 3.2. Local tolerability at the site of administration will be carefully considered.

All Adverse Events will be described in the Listing 7.

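### The single causality rating is labelled as relation to the product but defined as relation to device or procedures, so the product-related count cannot be read as device-related

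*Protocol*

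**What the plan says.** Protocol 14.2 opens the causality scale with "The relationship of any AE to the product will be classified by the Investigator as follows". Four levels follow, and each one names procedures as well as the device:

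- *Not related*: "Relationship to the device, comparator or procedures can be excluded".
- *Possible*: the relation to device or comparator, "or the relationship with procedures, is weak but cannot be ruled out completely".
- *Probable*: the relation to device or comparator, "or the relationship with procedures, seems relevant and/or the event cannot be reasonably explained by another cause".
- *Causal relationship*: "The adverse event is associated with the investigational device, comparator or with procedures beyond reasonable doubt".

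Protocol 7.3.6 and SAP 12.2 then count subjects with "study product-related AE or ADE, serious AE or ADE, severe AE or ADE"; the SAP places this in Table 3.1. SAP 12.2 also promises "additional grouping by severity and relationship to the study treatment in the Table 3.2".

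The SAP mock table for adverse events (14.4.4) has one relatedness item, worded as relatedness to study treatment. It has six levels: Certain, Probable, Possible, Doubtful, None and Unknown. Neither document says which levels make an event product-related, and neither describes a separate rating for the procedure.

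**The concern.** The question put to the investigator is about the product, but the answer categories are about product or procedure. The summary takes its name from the question, while its content follows from the categories.

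In this trial the difference is not academic. Each session consists of multiple microinjections, there are three sessions, and anaesthetic cream may be used (Protocol 6.2.1 and 6.2.1.2). Protocol section 4 expects the injections themselves to cause trouble: "Injections, even if done with micro needles could generate some risks and a certain level of discomfort to the subject". The four local reactions singled out in the safety endpoints are ones that a needle can produce without any contribution from the gel. A reader of Table 3.1 will take the product-related line as a statement about Foliage Hydrofil, and by the protocol's own definitions it is not one.

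**Working it through.** There is no stated figure to reproduce. The check is mainly textual, followed by an illustration under assumed rates.

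**1. Rate a needle-only bruise on the Protocol 14.2 scale.** Suppose the investigator is certain that the needle caused it and the gel did not.

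- *Not related* is unavailable on its natural reading, because the procedures cannot be excluded.
- *Possible* does not fit, because the relation to procedures is not weak.
- *Causal relationship* fits, because association with procedures beyond reasonable doubt is enough.

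**2. Follow the rating into the tables.** The level cut-off for product-related is undefined. Any plausible cut-off includes the top level, so a certain needle event is counted under all of them. A less certain needle event, rated *Possible*, is counted only if that level is included; that part is inference.

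**3. Look for something that separates the two sources.**

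- The adverse device effect category does not. Its definition in Protocol 14.1 covers deployment of the device and user error, the summaries pool it as AE or ADE, and the mock tables (SAP 14.4.4 and 14.4.5) have no row for it.
- Local tolerability does not. Protocol 7.3.6 says that it will be summarised, but SAP 12.2 says only that it will be considered, and SAP 14.3 lists no table for it.
- The mock for the SOC and preferred-term display (SAP 14.4.5) shows no relationship column.

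**4. Compare the scales.** The protocol has four levels and the SAP mock has six. *Doubtful* and *Unknown* have no counterpart in the protocol.

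**5. Illustration A: needle events only.** Inputs: 24 subjects and three sessions (documents); needle-event rate p per session (assumed, no source in the documents). If sessions are independent, the share of subjects with at least one such event is 1 − (1 − p)³. If a subject's sessions are perfectly correlated, the share is p.

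| p per session | Independent | Of 24 | Perfectly correlated, of 24 |
|---|---|---|---|
| 10% | 1 − 0.9³ = 27.1% | 6.5 | 2.4 |
| 30% | 1 − 0.7³ = 65.7% | 15.8 | 7.2 |
| 50% | 1 − 0.5³ = 87.5% | 21.0 | 12.0 |

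Every subject in the table would be counted as product-related with no gel effect.

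**6. Illustration B: both sources present.** Let 10% of subjects have a device-caused event (0.10 × 24 = 2.4) and let a share q have a needle-only event, independently; both are assumed. The share labelled related is 1 − 0.9 × (1 − q).

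- q = 25%: 32.5%, or 7.8 of 24.
- q = 50%: 55%, or 13.2 of 24.
- q = 75%: 77.5%, or 18.6 of 24.

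If needle events are common, they dominate the count.

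**The case against.** The best reply is that the trial does not set out to study the gel apart from its injection. Protocol 5.3 frames local safety at the injection site, and safety of the treatment. The product is made to be injected, a needle comes in its package (Protocol 6.2.1.1), and Protocol section 4 lists the four local reactions as potential effects of the treatment. The safety endpoints are number, type and severity of events, and the product-related count is one line among several. Pooling also over-attributes rather than hides: a reaction to the gel is still counted.

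Most of this stands. A reader might infer that the device's local safety cannot be read at all. The documents do not support that. All events are summarised by SOC, preferred term and severity whatever their causality, so the overall burden of pain, erythema, edema and bruising remains visible. The grouping planned for Table 3.2 and the item in the mock table refer to study treatment, which suits a combined rating.

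Three further limits are fair:

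- The mention of a comparator in a single-arm study suggests generic scale wording, and the lead-in could steer an investigator to rate the product only. Ratings may then differ from one event to the next, which does not rescue the label.
- The eCRF is not among the documents, so a separate procedure field cannot be ruled out; none is described.
- The assumed rates have no source, and positive correlation between sessions lowers the results.

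What the reply does not answer is the word *product* on a count whose definition includes procedures.

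**Conclusion.** The point holds as a mislabelled safety summary. Under Protocol 14.2 an event attributed with certainty to the needle alone is a *Causal relationship* and falls in the product-related count of Protocol 7.3.6, SAP 12.2 and Table 3.1. That count is device plus procedure and cannot be read as device-related. The loss is confined to the device/procedure split in the related summaries; the primary endpoint is untouched.

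The size cannot be derived from the documents. The illustrations show only that the effect could range from a few of the 24 subjects to most of them, depending on needle-event rates that are assumed. They also assume that every such event is recorded, is rated at a level that counts as related, and that all subjects receive three sessions.

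It would also go too far to say that a second rating would measure the gel's effect. With one arm, open label and no needle-only control, it would record the investigator's opinion.

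**What to change.** **Firm change, wording only.** In SAP 12.2 and Tables 3.1 and 3.2, call the summary *device- or procedure-related*. State which of the four Protocol 14.2 levels count as related, and replace the six levels in the mock table with those four. SAP section 2 says that the plan is finalised before database lock, so this can be done without touching the data.

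**Where events can still be rated.** Record causality twice on the same four levels, once for the device and once for the procedure (needle, disinfection, anaesthetic cream), in Protocol 14.2 and the eCRF. Build the product-related summary from the device rating only, and give procedure-related events their own row. SAP section 7 reports the 24 subjects as already recruited, so this may apply to few events or none.

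**Cost.** The relabelling costs a few lines of text. The split costs one extra field per event and one table row. The investigator makes two judgements, some events will be *Possible* on both, and the result remains judgement rather than a measured separation.
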